1.6.2 Specific Objectives

1. To understand the perspectives of stakeholders (school teachers, administrators, parents, community leaders and students) on a school-based FA training (YoFA) program among SSC.

Hypothesis 1: The perspectives of stakeholders like school administrators, teachers, parents, community leaders, and school children needs to be understood to design a comprehensive YoFA program

2. To assess school children's Knowledge, Attitudes (willingness to) and Practices (self-efficacy) (KAP) on trauma/injury FA via the built YoFA training to stop LTBs.

Hypothesis 2: School children have limited knowledge, self-efficacy and practices regarding trauma/injury FA

3. To evaluate the effectiveness and usability of the YoFA training program for SSC to respond to LTBs safely and promptly in their environs.

Hypothesis 3: The YoFA training Program is effective in improving the KAP of SSC and it is usable within the school and community setting.

4. To determine the barriers associated with implementing the YoFA program among early SSC in the Fako Division.

Hypothesis 4: There exist some barrier/challenges in implementing a YoFA training

program in secondary schools.

CHAPTER TWO

LITERATURE REVIEW

It is important to understand some aspects regarding first aid training for children in schools. Here, we will be highlighting the relevance of Advanced Trauma Life Support concepts, the injury burden among school children, the qualifications of potential educators, and the appropriateness of school-based training. There is a clear consensus on the necessity and benefits of teaching first aid in schools, as it equips children with essential life skills, enhances their confidence, and promotes a safer environment. Future research should focus on developing effective training programs tailored to this age group, considering the emotional aspects of learning and the varied contexts in which children may need to apply their skills particularly in our setting.

First aid training is an essential aspect of emergency preparedness, particularly for children aged 10 to 14 years. This age group is increasingly exposed to various risks, both in schools and everyday life. Here, we will explore four key areas related to first aid training for children: the concept of Advanced Trauma Life Support (ATLS), the injury burden among school children, potential educators of first aid, and the appropriateness of implementing first aid training in schools.

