3.5 SAMPLE SIZE AND SAMPLING

Sample Size Calculation

For the cross-sectional study and Intervention

Assuming an equal number of control and intervention subjects, a prevalence of the outcome in the controls of 0.5, and a prevalence in the intervention group of 0.75 (an absolute increase of 25%)[17] with a power of 80% and 5% error margin, we calculated the sample size needed using STATA.

Estimated sample sizes for a two-sample proportions test Pearson's chi-squared test using STATA

$H_0: p_2 = p_1$ versus $H_a: p_2 \neq p_1$ Study parameters:

```
alpha = 0.0500
power = 0.8000
delta = 0.2500 (difference)
p1 = 0.5000
p2 = 0.7500
```

Estimated sample sizes:

N =	116
N per group =	58

If we assume a 15% drop out rate, we have a sample size of $15\% * 116 = 17.4$ Thus, sample size is $116 + 17.4 = 133.4 \approx 134$

For each group, the sample needed is therefore **N = 67 students. Sampling**

Since this is a crisis area, we will use convenience sampling to choose the Health Areas (HAs) that are secure and geographically accessible (safest) in both HDs. Out of seven (7) and eight (8) HAs in Buea and Tiko HDs respectively, there are 4 accessible HAs in each. Of these, one HA from each HD does not harbour a state secondary school (SSS).

Leaving us with 3 HAs to work with in each HD. Each of these HAs contains 1 SSS but for 1 HA from each District which has 2 SSSs. We would work with all these State schools to ensure that we get students from most of the communities around the schools, thus ensuring the representativeness of our samples. To avoid spill-over, one of the districts will be selected as intervention HD and the other as the control.

Stratified random sampling will be used to select the students for the study from a sampling frame of the list of students in each classroom concerned.

We would use probability proportionate to size to choose the specific number of students to participate in the study per classroom (A, B, and C) for each class.

[figure not shown]

Figure 5: Selection of HAs and Schools for Implementation.

*GHS-Government High School; BGS-Bilingual Grammar School; GTHS Government Technical High School; GBHS government Bilingual High School

For each school distribution of the participants will be as follows:

A) For the Qualitative part:

The qualitative part will be sampled purposively.

Table 2: Number of Participants to be chosen per school for the FGDs

Health District	Schools	FGD Category of Participant	Number per school

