will be a session for pretesting at the beginning of the intervention, at the immediate end, and 3 months after. **During the 3 months follow up period, we will visit the schools during their Wednesday club days every 2 weeks for 30mins to 1hour, to document their experiences and challenges in real time and their use of the skills.**

The qualitative part will take place before the quantitative pretesting of both groups begins.

Table 6: Plan of training and Evaluation of intervention groups

HA	School	N	Training Period in 2024	Date for Last Evaluation, 2024
Molyko (Intervention)	BGS Molyko	25	Nov 6 th , and 13 th	Feb 5 th
		25	Nov 20 th , and 27 th	Feb 19 th
		25	Dec 4 th and 11th	March 5 th
Mutengene (Control)	GHS Mutengene	70	November 6 th	Feb 26 th
	Total	145		

Step 3: Evaluation Phase

This comprises the evaluation of students' perceptions, barriers, and challenges in learning and applying the skills and lessons learned. It will equally involve evaluating parents' and stakeholders' perceptions about the program and including FA training in school curricula. It will involve the use of evaluation forms. This will take place about the same time as the post-three-month evaluation.

Knowledge will be assessed by evaluating whether the participants have ever heard of first aid or observed situations in which first aid was needed. They will be expected to have an increase in knowledge of first aid, especially regarding calling for help, stopping acute and life-threatening bleeds (LTB), and referrals after the training.

Before the training, we expect people not to have practiced first acts ever or to have

done it in a wrong way or to be scared to carry out specific first aid acts. After the training, we expect them to be more alert and identify situations needing first aid acts. Additionally, we expect their self-efficacy and confidence to perform first aid acts to increase and to effectively carry out first aid acts within their community or the school premises that will be documented using designed forms.

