3.11 DATA ANALYSIS PLAN

A difference-in-difference analysis would be done to assess the change in KAPs before and after the intervention in. The posttest would be done immediately after the 4 days of training for each pool and 3 months after the training to assess the need for refresher course planning.

The exposure variables include training on LTBs from injury first aid and the use of these services by the trained students (e.g., the number of persons assisted or referred during the follow-up period of the training).

We will analyze survey data using R Software with a combination of descriptive statistics and parametric and non-parametric tests to establish statistically significant differences between pre- and post-test results and between the intervention and control groups.

Table 7: Objectives and their Indicators

Objective	Activities/process	Data collection tools	Data Source	Indicators
1. To understand the perspectives of stakeholders on YoFA training program among SSC	- In-depth interviews	-In-depth interview guides	School teachers, administrators, parents, community leaders and students	
2. To assess school children's KAP (willingness and self-efficacy on trauma/injury FA via the built YoFA training to stop LTBs.	- survey	-Questionnaire	- students	- Obtain baseline KAP Scores
3. To evaluate the effectiveness and usability of the YoFA training program for SSC to respond to LTBs safely and promptly in their environs.	-Training following a specific STB and LFRs program -Training students on specific modules of LTB FA - Pre and post test -Simulation exercises	- Use adapted tools from the SBEAT - Questionnaires - Evaluation form with questions how? What was the situation?where, and how?	Stakeholders, teachers, parents, students	- Change in knowledge scores -At least 50% of stakeholders rate the program as good/ expectations met - 70% of students rate the program as good/expectations met - Number of children who made use of the FA skills taught
4. To determine the barriers associated with implementing the YoFA program among early SSC in the Fako Division.	- Interviews - Survey	-Interview guides - Questionnaires	- Stakeholders, - Teachers, students	- Perceived reasons and challenges that hinder FA training in schools.

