3.12 ETHICAL CONSIDERATIONS

This research will prioritize the ethical principles of informed consent, confidentiality, and respect for participants. All participants will be informed about the purpose of the study and their right to withdraw at any time. Parental consent will also be obtained from the students before carrying on with the trainings. Confidentiality of information obtained from participants will be strictly maintained, and ethical approval will be sought from the institutional review board of the Faculty of Health Sciences of the University of Buea.

NB: Following the research study, all the children within the various schools will be retrained on the program to ensure equity.

Potential risks and Mitigation Strategies

Risks	Mitigation Strategies
Breach in confidentiality	No names on the pre and post-tests, only initials to be able to measure the degree of KAP change, no other potential respondent will come in contact with the filled questionnaires
Loss of time	-The tests are administered by data collectors using filling will be faster Duration: 30mins only. -For the qualitative part, the participants will be informed ahead of time so that their convenience is met.
Psychologic risks related to filling of the questionnaires or taking tests and responding.	Questions in the tests will be simply focused on what will/has been taught and in very simple languages with explanations given to the entire group at once if clarifications needed. Respondents will be counselled prior to the interviews and be given liberty to back out at any moment.
Difficulty interacting during interviews since some people are not used to being recorded.	Interviews will be performed at convenience of the interviewee. The interviewees will also be allowed to ask questions and the research team will answer all questions in line with the study.

Potential Benefits

For the Participants:

- They will be first in the secondary schools in the Southwest to benefit from such knowledge and skill set.
- They will have the opportunity to apply the knowledge and skills learnt among their peers and the communities where they live.
- They shall each benefit from a transport for the evaluation phase.

The population:

- They shall be the first to benefit from such services in the advent of traumatic injuries and these will be free of charge.
- They will contribute ideas to help improve on the YoFA program.

The country:

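### The risk table covers data collection only, and no indicator measures the helping pupil's safety, although objective 3 asks for a safe response

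*Protocol*

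**What the plan says.** The risk table in section 3.12 has four rows: "Breach in confidentiality", loss of time, "Psychologic risks related to filling of the questionnaires or taking tests and responding", and "Difficulty interacting during interviews since some people are not used to being recorded".

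The same section names, as a benefit to participants: "They will have the opportunity to apply the knowledge and skills learnt among their peers and the communities where they live". Section 3.6, Step 3, expects trained pupils to "effectively carry out first aid acts within their community or the school premises that will be documented using designed forms". Section 3.7 makes the number of participants who use the skills in the three months after training an outcome variable, and Table 7 in section 3.11 repeats it as an indicator for objective 3.

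Objective 3 in section 1.6.2 concerns the effectiveness and usability of the programme for pupils "to respond to LTBs safely and promptly in their environs". Among its data collection tools, Table 7 describes an "Evaluation form with questions how? What was the situation?where, and how". Section 3.6, Step 2, adds school visits every two weeks during follow-up to record pupils' experiences, challenges and use of the skills. Section 3.3.2 names staying safe as one focus of the quantitative part.

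**The concern.** Use of the skills on a real bleed is an intended effect of the training, so any risk attached to it is a risk of the intervention. The protocol treats such use as a benefit and an outcome, but does not carry it into the list of risks. It also sets an objective with two qualities, safe and prompt, and provides a measure for only one of them.

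The stake is the balance of the final report. Chapter Four says the results will be used to judge scalability and uptake into health and education policy, and section 3.12 plans training for all children in the schools afterwards. If training leads pupils to step in more often, the report should show what happened to those pupils as well as how many helped. Without a defined item, an absence of reported harm could not be told apart from harm that was not systematically sought.

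**Working it through.** No stated figure needs reproducing. The check is a count of what each list contains, followed by a comparison with objective 3.

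**1. Risk table (3.12).** Confidentiality, time, stress from questionnaires or tests, discomfort at being recorded. Rows about the training or its use at a real scene: 0 of 4. Chapter Two reports concern about children's emotional readiness for traumatic situations; the table confines psychological risk to forms, tests and responding.

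**2. Outcome variables (3.7).** Knowledge change, test scores, self-efficacy, response time, number using the skills. Harm to the pupil: 0 of 5.

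**3. Success criteria (3.6, Step 3).** Emergency calls made, people who received help, bleeds attended to or referred, intention to act, performance in scenarios. The criteria on real events concern the call made or the person helped. Harm to the pupil: 0 of 5.

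**4. Indicators (Table 7).** Objective 2 has one (baseline scores). Objective 3 has four (change in knowledge scores, stakeholder rating, student rating, number using the skills). Objective 4 has one (perceived challenges). Objective 1 has none. Total 1 + 4 + 1 = 6. Pupil safety: 0 of 6.

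**5. Operational definitions (1.1.2).** Seven terms are defined. Injury response time is the promptness measure, taken in simulated scenarios. Practical skill is rated on accuracy and confidence. None defines a safe response, simulated or real.

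**6. Instruments (3.8).** In the legible text of the questionnaire and the ten-item usability scale, no item asks whether the pupil was hurt or had contact with blood. Some picture items are not shown, so this covers the text only.

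**Objective 3, side by side**

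| Quality in the objective | Measure in the protocol |
|---|---|
| Prompt | Response time (1.1.2, 3.7) |
| Safe | None stated |

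**7. Routes by which harm might still surface.** The two-weekly visits, and the evaluation in section 3.2 that identifies challenges met during the three months, could bring out an injury if a pupil mentions it. Neither text defines harm, prompts for it, or assigns it a count or a place in the results.

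**The case against.** The strongest reply is that the hazard is not ignored. Staying safe is part of the content, the parent and teacher guide asks what would make the training safe to conduct, and the exploratory design lets those answers change the programme. The two-weekly visits give pupils a regular chance to report trouble. This stands as far as it goes: the hazard is touched on in content and design, and an injury could well come to light. But teaching a precaution does not record whether harm occurred, and unprompted mentions give no usable numerator.

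Several stronger readings are tempting, and the documents do not support them:

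- *The event form excludes harm.* Table 7 gives only a shorthand description, and the forms mentioned in section 3.6 are not reproduced. One can say that no harm item is specified, not that the form has none.
- *The trial is bound to report helping without harm.* The visits make that uncertain.
- *Parents are not told of this risk.* The consent pages are not available here, so their wording cannot be judged.
- *The setting makes the danger acute.* Section 3.5 does say "Since this is a crisis area, we will use convenience sampling", but the sentence goes on to limit the choice to secure and accessible health areas. It is about site selection.
- *A numerical bound on the risk.* The protocol gives no rate at which pupils will act, and much of the counted use is calling or referring, which need not involve contact with blood. Any figure would rest on an invented rate.

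It is also fair to say that hypothesis 3 concerns knowledge, attitudes, practices and usability, and that no primary comparison changes. The wording of objective 3 remains, and only data collected under the protocol can answer it.

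**Conclusion.** The point holds in a limited form. The risk table omits risks that come from the intervention, and the safety part of objective 3 has no outcome, criterion or indicator. This is a gap between an objective and its measures, visible within the protocol itself; it cannot be left to an analysis plan, because unrecorded events cannot be analysed later.

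Its size is the set of zero counts above, not an event rate: the document gives no basis for estimating how often a helping pupil would be hurt or exposed. Sample size, schedule and main comparison are unaffected. The conclusion assumes that the unseen forms contain no defined harm item tied to a reported result. If they do contain one, the missing risk row and the missing indicator still need correcting.

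**What to change.** 1. **Section 3.12:** add a row for risks to the pupil from acting at a real scene, with its mitigation, and check that the information given to parents agrees with it.
2. **Event form and two-weekly visits, in both schools:** add two prompted items for each event: was the pupil hurt (yes/no, and how), and was there blood on bare skin (yes/no).
3. **Table 7, objective 3:** add the number of pupils harmed or exposed among those who acted, by arm, beside the number who used the skills.

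The cost is one table row, two short items on recording already planned, and one line in the results. The drawbacks are slightly more recording and a possibly less favourable picture of the programme. Asking in both schools matters because untrained pupils may also step in, and the comparison needs the same question in each arm.

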4.1 LIMITATIONS

Data source (DHIS 2) to enable the choosing of the districts with the highest number of trauma and injury cases may not be accurate due to the poor and incomplete reporting of trauma and injury cases in the system.

Private schools were not involved in the study given that they have slightly different school programs from the rest of the public schools.

Result Dissemination Plan

The results of the research will be shared with the wide public particularly the community of researchers in various journals, the institutions that granted administrative authorization and the Ministry of Public health through its Health Districts.

This will specifically be shared through publication in Scientific Journals and Reports. International spread will be important to enable philanthropists see the felt need of first aid in our setting and act accordingly to bolster overall health care in the world.

It will also be shared with the Ministries of Education so that they can consider incorporating First aid in the regular curriculum of schools.

Specific measures for vulnerable participants

Vulnerable participants will be attended to base on their vulnerability and resources available. For example, parents who are not literate can make a phone call to the principal investigator before giving consent. Also, children who are blind will be read the questions. However, the schools selected are less likely to have blind students there in

Alongside the school, the research team will determine ways to manage vulnerable participants without giving room for biases of any kind.

Procedure and framework for soliciting informed consent

Informed consent will be obtained from parents via two main ways:

- During Parents' Teachers Association (PTA) meetings where the consent forms will be read together with the parents before they can give their consent. OR
- Via mails (Letters in envelopes) sent to parents through the children with a specific date of return. The envelopes will contain the information notices and the consent forms where in the contact and address of the PI will be noted in case parents needed more clarity.

TIMELINE

Table 5: Timeline

REFERENCES

